Besides issues of tolerability, there are other reasons for primary use of ECT (in the absence of prior medication failure in the current episode). These issues include a history of poor medication response and good ECT response in prior episodes, urgency for rapid remission due to psychiatric (suicidality) or medical (inanition) reasons, and patient preference. The American Psychiatric Association Task Force on ECT (APA, 2001) detailed the circumstances when ECT should be considered as a primary (first-line) treatment and when it should be reserved for patients with established medication resistance. These considerations will guide patient selection in this protocol and the rationale for use of FEAST will be documented.

A factor strongly related to medication resistance is episode duration. Patients with more chronic episodes (longer duration) tend to have poorer outcome with ECT (Nobler and [name], 1996). When both medication resistance and episode duration are considered simultaneously they make independent statistical contributions to outcome prediction. Age also has shown consistent relations [see ([name], 2004b) for a review]. Surprisingly, the majority of studies have found a positive association between advancing age and ECT outcome, one of the few instances in medicine where older patients have superior outcome. Due to problems of medication tolerance with advanced age and the toll of severe episodes of depression, ECT is particularly likely to be recommended in older individuals (Olfson et al., 1998, Thompson et al., 1994).

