The protocol presented in this new IDE will be performed at two clinical sites (MUSC and GRU). At each site 20 patients will be recruited to receive treatment with FEAST, or a total of 40 FEAST patients across the sites. A contemporaneous group of 20 patients will be identified at each site who are receiving standard clinical treatment with UB RUL ECT. These patients will be matched to the FEAST sample (within site)

in the distribution of gender and diagnosis (unipolar vs. bipolar), and the mean, variance and shape of the distributions of age and baseline modified mini-Mental State score (mMMS) (Stern et al., 1987). This RUL cohort is also included under this IDE. [We considered but ultimately abandoned having a formal, blind randomization of patients to FEAST or RUL. While we ultimately hope to perform such a study, the data with FEAST are quite limited at present. There thus may not be true clinical equipoise. Similarly, although the FEAST side effects appear benign, there have still been less than 50 patients total ever treated with FEAST. We thus have settled on a non-randomized but loosely matched comparison group. This group is important for the analysis of the EEG and MRI data, and can also be used for rough comparison of efficacy and cognitive side effects. It is our hope that following this trial, there might be sufficient evidence of efficacy to enable a formal randomized definitive trial.

We will be applying to the NIH for funding to support the conduct of this protocol. This IDE will serve to gather important pilot data and will serve as the IDE for the NIH study, if it is funded.

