The primary aim of this study is to contrast FEAST and UB RUL ECT in these EEG measures of seizure onset and propagation. Specifically, we expect FEAST to show greater focality of seizure onset than UB RUL ECT, with seizure onset most manifest in the right frontal EEG with FEAST, and far greater activity in the left and right temporal leads with UB RUL ECT.

B.14 Quality Assurance and Data Management

A highly experienced rater will provide clinical ratings throughout the treatment period. Accuracy of the output of the FEAST device will be tested ([name] et al., 1994), and calibration signals regularly applied to the EEG recordings. The stimulus parameters used with the modified Spectrum 5000Q will both be recorded electronically and transferred to a database using the Spectrum's automatic EMR logging software. An experienced psychometrician will review all neurocognitive data. Data will be entered on digital forms using automatic flags for out-of-range and missing values. Any correction to a data record will be recorded in an audit notebook. The study database will be backed-up regularly.

B.15 Statistical Analyses

Data Screening. Data will be reviewed for extreme values. When distributional assumptions are not met, data will be transformed or nonparametric procedures used. Prior to statistical analyses, the study sites (MUSC vs. GRU) and treatment groups (FEAST vs. UB RUL ECT) will be compared in the baseline sociodemographic and clinical features, using ANOVA and log-linear analyses, with a liberal threshold to detect inequality ($P < 0.2$).

Hypothesis Testing. Even though this is a preliminary investigation, yielding effect sizes by which to power a subsequent randomized study, it is important to protect the Type I error rate by limiting primary analyses to a restricted and clearly specified set of hypotheses and outcome measures. The primary analyses will test the hypotheses stated below which address the objectives described in Section II. The major areas of investigation are effects on seizure threshold, electrophysiological (EEG) activity, efficacy, function, objective changes in cognition and subjective cognitive changes. The primary efficacy analyses will be conducted in the intent-to-treat sample.

Hypothesis 1. FEAST is substantially more efficient (i.e., lower ST) than traditional ECT, even when both use an ultrabrief (0.3 ms) pulse width.

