The primary analysis for Hypothesis 4 will use all available HRSD₂₄ data (i.e., the intent-to-treat data) from the FEAST and UB RUL ECT samples. A random regression model will be used to examine the relationship between HRSD₂₄ scores and treatment group. Time will be the within-subjects repeated measures factor, site and treatment group the between-subjects factors, with medication-resistance classification and baseline HRSD₂₄ serving as covariates. All interactions with time will be modeled. In secondary analyses, we will also include age, gender, age-at-onset of illness, and duration of current episode as covariates, if pre-screening indicates utility. We will investigate whether HRSD₂₄ scores are linear in time or quadratic, cubic, or piece-wise linear (e.g., hockey-stick shaped). Indeed, in a study comparing several different statistical methods in their sensitivity to ECT treatment groups differences in rate of clinical improvement, we found that the HRSD₂₄ scores over time were frequently nonlinear (Nobler et al., 1997a). The type of analysis conducted on HRSD₂₄ scores will be repeated for secondary analyses with the MADRS, IDS-SR, and CGI-S.

FEAST and UB RUL ECT will also be compared in the categorical outcomes of final remission status (HRSD₂₄ of 10 or less at post-treatment) in a secondary analysis to gauge generality of the effect and clinical significance. Nominal logistic regression analysis will be used to compare the treatment groups in covariate-adjusted odds of remission. Remission status will be the dependent variable. The independent variables will be the treatment group indicator, along with site, medication resistance, and baseline HRSD₂₄.

Hypothesis 5. In two primary cognitive measures, orientation recovery time and CUAMI-SF scores, FEAST will have a significant advantage relative to UB RUL ECT.

The cognitive measures were described in Section B.12. Orientation time will be averaged within each patient across all treatments. An ANCOVA will be conducted on these values with Site and Treatment Group as between-subject factors, and age and number of treatments in the average as covariates. A similar ANOVA will be conducted on CUAMI-

SF scores, with Site and Treatment Group as between-subject factors, and age, number of treatments, and baseline CUAMI-SF score as the covariates.

Hypothesis 6. FEAST will have a significant advantage in the subjective global evaluation of the effects of ECT on memory.

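### The primary Hypothesis 4 efficacy model omits duration of the current episode, an unmatched predictor that the protocol says acts independently of medication resistance; age, loosely matched, is left out of this model alone.

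*Combined protocol and SAP*

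**What the plan says.** Section IV.B.15, Hypothesis 4, sets out a random regression model for HRSD24 with time, site and treatment group, "with medication-resistance classification and baseline HRSD₂₄ serving as covariates", and all interactions with time. Other covariates are left to secondary analyses: "we will also include age, gender, age-at-onset of illness, and duration of current episode as covariates, if pre-screening indicates utility". The plan does not say what the pre-screen tests or what result counts as useful. The remission logistic model has treatment group, site, medication resistance and baseline HRSD24, with no provision for adding to them.

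Section III.B.3 discusses predictors of ECT outcome. On episode duration it says "Patients with more chronic episodes (longer duration) tend to have poorer outcome with ECT" and then "When both medication resistance and episode duration are considered simultaneously they make independent statistical contributions to outcome prediction". On age it says "Age also has shown consistent relations" and that "the majority of studies have found a positive association between advancing age and ECT outcome".

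The study overview before section IV.B matches the groups within site on gender, diagnosis, and "the mean, variance and shape of the distributions of age and baseline modified mini-Mental State score". Episode duration and medication resistance are not matching factors. The overview itself describes the matching as loose. Section IV.B.1 states that the study is open label, non-randomised and unmasked.

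**The concern.** The protocol names two variables that predict outcome independently of each other. The primary model takes one, medication resistance, and leaves out the other, episode duration. Duration is therefore controlled neither by the matching nor by the primary analysis. Its only route into an efficacy model is a secondary analysis that depends on an undefined look at the data.

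Age is in a better position because its distribution is matched. Still, the models for Hypotheses 1, 2, 3, 5 and 6 all fix age as a covariate in advance. Hypothesis 4 does not, and no reason is given.

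This matters because FEAST patients choose FEAST, while comparison patients are those already scheduled for right unilateral ECT. The two groups could well differ in chronicity. Hypothesis 4 predicts no difference in efficacy, so confounding could hide a real loss of efficacy as easily as create a false one. Section IV.B.15 also says the study is meant to yield effect sizes for powering a later randomised trial, so a biased contrast would carry forward.

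**Working it through.** **1. The passages side by side.**

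| Variable | Section III.B.3 | Matched | Primary H4 model | Remission model |
|---|---|---|---|---|
| Medication resistance | Independent contributor, with duration | No | Yes | Yes |
| Episode duration | Independent contributor, with medication resistance | No | No; secondary and conditional | No |
| Age | Consistent relation with outcome; not called independent | Distribution, within site | No; secondary and conditional | No |

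Episode duration is the one named predictor that neither the design nor the primary model handles.

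**2. Illustrative size.** The plan gives no power, margin or effect size for Hypothesis 4, so there is no figure of its own to reproduce. For an omitted covariate:

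bias = r × d × SD

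- SD = 10.9, the pilot post-treatment HRSD24 SD (section I; section III.D.6 gives 11.2 for all 17 patients).
- r = correlation of the covariate with outcome, assumed 0.2 to 0.4.
- d = between-group imbalance in SD units, assumed 0.2 to 0.5.

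Results:
- Low end: 0.2 × 0.2 × 10.9 = 0.44 points.
- Middle: 0.3 × 0.3 × 10.9 = 0.98 points.
- High end: 0.4 × 0.5 × 10.9 = 2.18 points (2.24 with SD 11.2).

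For scale, with 40 per group the unadjusted 95% half-width is 1.96 × 10.9 × √(2/40) = 4.78 points. The bias does not shrink as the sample grows.

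**3. Allowing for medication resistance.** Section III.B.3 says episode duration is strongly related to medication resistance, which is already in the model. Assume r = 0.3 for each with outcome, a correlation of 0.5 between them, and a resistance imbalance of 0.5 × d.

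- Coefficient of duration given resistance: (0.3 − 0.5 × 0.3)/(1 − 0.5²) = 0.20.
- Imbalance in duration left after adjusting for resistance: d × (1 − 0.5²) = 0.75d.
- Remaining bias: 0.20 × 0.75d × 10.9 = 0.15 × d × 10.9, half of the unadjusted 0.3 × d × 10.9.
- For d = 0.25 and 0.4 the bias falls from about 0.8 and 1.3 points to about 0.4 and 0.65.
- Outcome variance explained by adding duration falls from 0.3² = 9% to 0.20² × 0.75 = 3%.

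**4. Cost in the models.** All interactions with time are modelled, so each added covariate brings a main effect and at least one time interaction: at least four terms for two covariates, and more if time is nonlinear. For remission, assume the pilot rate of 5/17 in both groups and 80 patients: 80 × 5/17 ≈ 24 events. That is about 6 per predictor with the present four, 4.7 with five and 4 with six.

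**The case against.** The case for leaving the plan alone has several parts.

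- The efficacy comparison is not the main aim. Section IV.B.5 ranks it below the EEG comparison, and section III.D.2 calls the efficacy data preliminary. This limits the stakes. It does not justify omitting a known predictor, because section II still names HRSD24 the primary efficacy measure and section IV.C.2 regards possible lack of efficacy as probably the main risk of FEAST.
- The primary covariates are pre-specified, and the disputed ones are named in advance. This is true. What remains is their secondary placement and the undefined condition.
- Medication resistance already absorbs part of any duration effect. This stands, and step 3 of the working shows that it could halve the bias. It cannot remove it if duration contributes independently, as the protocol says.
- Age is matched. This stands, and makes the age half of the point weaker.

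Three stronger readings are tempting, and the documents do not support them.

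- A reader might infer that the protocol calls age an independent predictor. The statement on independence covers only duration and medication resistance.
- A reader might infer that the baseline comparison at P < 0.2, described under Data Screening as made "with a liberal threshold to detect inequality", decides which covariates enter Hypothesis 4. The plan never links the two, and the pre-screen could equally be a test of association with outcome. Such a baseline test would miss a 0.25 or 0.4 SD imbalance 56% or 30% of the time at 40 per group (46% or 18% at 60). Those rates say nothing about the primary model, which omits duration whatever the test shows.
- A reader might take the change to cost only two degrees of freedom. The time interactions make it more.

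**Conclusion.** The point holds, most firmly for episode duration. By the protocol's own account duration predicts outcome over and above medication resistance, yet it is neither matched nor in the primary Hypothesis 4 or remission model. Its secondary use rests on an undefined, data-dependent condition. For age the point is one of consistency: it is loosely matched, related to outcome, and left out of this model alone among the six.

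The illustrative bias is about 0.4 to 2.2 HRSD24 points before allowing for the adjustment for medication resistance, and roughly half that under the assumptions of step 3. The correlations and imbalances are assumed, and the SD comes from a small pilot of FEAST patients only. The documents do not say how the groups would differ, so the direction is unknown. The change should be made because it is cheap and removes the part of the confounding that runs through measured variables, not because a large bias has been shown.

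**What to change.** - In the primary Hypothesis 4 model, pre-specify log episode duration, and age as in the other five models, alongside medication resistance and baseline HRSD24. The log is sensible because pilot duration was 225.7 ± 257.3 weeks (section III.D.6), an SD larger than the mean.
- Delete the pre-screening condition. Keep the model without duration and age as a sensitivity analysis.
- Add episode duration to the remission logistic model. Add age there only if the number of remission events supports it.
- Report baseline balance between groups as standardised differences.

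Cost: a wording change to section IV.B.15, at least four more terms in the primary model, and fewer events per predictor for remission. The plan already names both variables as candidate covariates, so no new data are needed.
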